7.3.5. Phase 1 Individual Patient Stopping Rules

The following safety events will trigger individual patient treatment discontinuation:

- Any DLT observed during Phase 1, within 28 days after starting treatment with TP-0184 as described in [Section 7.4](#)
- Any related AEs that lead to treatment discontinuation per [Section 7.4](#)
- Evidence of disease progression based on IWG Response Criteria for MDS 2006

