7.4.2. Dose-Limiting Toxicities

A DLT is defined as any one of the following events or abnormal laboratory value not clearly unrelated to the study drug observed within 28 days of starting treatment with TP-0184:

- Any death not clearly due to the underlying progression of disease (such as leukemic transformation)
- Any \geq Grade 3 non hematological toxicity except for Grade 3 of nausea, vomiting, diarrhea or clinically not significant lab abnormalities lasting 72 hours or less with adequate supportive care
- New onset cardiac failure or worsening symptomatic cardiac failure based on NYHA Functional Classification ([Appendix 11](#))
- ECHO or MUGA reduction of ejection fraction \geq 10%
- Any Grade 4 neutropenia (absolute neutrophil count (ANC) not recovering to $> 500/\mu\text{L}$ within 7 days in the absence of myelodysplasia or transformation to acute leukemia)
 - To determine progression of MDS / transformation to AML, a bone marrow biopsy / aspiration and/or peripheral blood can be performed
- Any Grade 3 thrombocytopenia associated with clinically significant bleeding or Grade 4 thrombocytopenia in the absence of myelodysplasia related marrow failure or transformation to acute leukemia
 - To determine progression of MDS / transformation to AML, a bone marrow biopsy / aspiration and/or peripheral blood can be performed
- All other hematological toxicity \geq Grade 3 other than defined above for ANC and platelets

Note: As Grade \leq 3 neutropenic and Grade 2 thrombocytopenic patients are included in the study, any new onset of Grade 4 neutropenia ($< 500/\mu\text{L}$ neutrophils) in a patient with prior history of chronic neutropenia with infection or Grade 3 decrease in platelets ($< 50\text{K}$ platelets) in patients with prior history of MDS-related thrombocytopenia with bleeding, will be evaluated by the SRC members and Medical Monitor in consideration as to whether a DLT has occurred. If determined that the Grade 3 or 4 hematologic AE is related only to the biology of MDS, no DLT will be declared.

Patients who experience a DLT during Cycle 1 will be discontinued from the study.

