8.3. Withdrawal Criteria

All patients have the right to withdraw at any time during treatment without prejudice. Circumstances may occur under which a patient may be permanently removed from the study. The criteria used to justify withdrawal of a patient are described in [Section 8.3.1](#).

An End of Treatment (EOT) visit will be conducted following permanent discontinuation of treatment with TP-0184 for any reason, except in the case of consent withdrawal by patient. The EOT visit will be conducted within 14 (± 3) days of treatment discontinuation, or within 14 days of the decision to discontinue TP-0184 treatment, as detailed in the Schedule of Assessments ([Table 6](#)).

If the patient withdraws consent for disclosure of future information, SDP Oncology may retain and continue to use any data collected before a withdrawal of consent. If a patient withdraws from the study, he/she may request destruction of any samples taken and not tested, and the Investigator must document this in the site study records, as well as notify SDP Oncology.

In the event of a treatment discontinuation, the assessments for the EOT visit and End of Study (EOS) visit, as detailed in [Table 6](#), should be completed wherever possible.

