8.3.1. Reasons for Treatment Discontinuation

A patient may be discontinued from TP-0184 treatment for any of the following reasons:

- In Phase 1, patient experiences a DLT during Cycle 1
- Failure to achieve a hematologic response. Patients not demonstrating evidence of hematologic response after the first 6 cycles (24 weeks) of treatment will be considered for treatment discontinuation, although with permission of the Medical Monitor and Investigator, TP-0184 study treatment may continue if clinically indicated and provided there is no evidence of Grade 4 toxicity.
- Grade 4 toxicity not responding to supportive measures and without a response to treatment
- The occurrence of any other AE, concurrent illness or laboratory abnormality which, in the opinion of the Investigator, warrants treatment discontinuation
- Patient noncompliance, defined as refusal or inability to adhere to the study schedule
- At the request of the patient, Investigator, SDP Oncology, or regulatory authority
- Patient is lost to follow-up
- Patient becomes pregnant while on study
- Patient begins another treatment for their disease
- Patient death
- Patient withdrawal of consent.

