8.3.2. Follow-up for Patients Discontinued from Treatment

In the event of a permanent discontinuation of treatment, the patient will be followed up for 30 (+ 7) days after administration of the last dose of treatment for safety assessments.

Follow-up for progression of MDS to higher risk and / or transformation to AML and survival will continue every 6 months for at least one year from start of treatment (Cycle 1 Day 1) with TP-0184.

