13.1.9.1. Efficacy Analysis

13.1.9.1.1. Phase 1 Efficacy Analysis

Phase 1 efficacy endpoints will be analyzed using Phase 1 Efficacy Analysis Set.

Efficacy analysis at Phase 1 will be conducted using similar methods defined in Phase 2 portion unless otherwise specified (details in [Section 13.1.9.1.2](#)).

Overall survival for Phase 1 is defined as the time from the date of initial dosing at same dose level or one dose level lower than RP2D to the date of death. Patients without documentation of death at the time of analysis will be censored at the date last known to be alive. Overall survival will be analyzed based on Phase 1 SAS patients.

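### Section 7.4.2 takes Cycle 1 DLT patients off the study where other sections stop only their treatment, so survival and AML follow-up of surviving DLT patients could be cut short

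*Protocol*

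**What the plan says.** The Protocol sets the consequence of a Cycle 1 DLT in several places.

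- Section 7.4.2 closes its DLT definition with: "Patients who experience a DLT during Cycle 1 will be discontinued from the study".
- Section 7.3.5 opens with "The following safety events will trigger individual patient treatment discontinuation" and lists first "Any DLT observed during Phase 1, within 28 days after starting treatment with TP-0184". Footnote b of Table 4, attached to Grade 3 non-haematological events, likewise stops treatment and says nothing about the study.
- Section 8.3.1 opens with "A patient may be discontinued from TP-0184 treatment for any of the following reasons" and its first entry is "In Phase 1, patient experiences a DLT during Cycle 1".
- Section 8.3 says "Circumstances may occur under which a patient may be permanently removed from the study" and refers to Section 8.3.1 for the criteria, although that section lists reasons for stopping TP-0184.

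Follow-up is set elsewhere. Section 8.3.2 states: "In the event of a permanent discontinuation of treatment, the patient will be followed up for 30 (+ 7) days" after the last dose, and then requires six-monthly follow-up for MDS progression, AML transformation and survival for at least one year from Cycle 1 Day 1. Table 6 footnotes b and c and Section 12.2.2 (survival) are to the same effect. None of them makes an exception for DLT patients.

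Overall survival (OS) and AML progression are Phase 1 secondary endpoints (Section 6.2). On the first, Section 13.1.9.1.1 says "Overall survival will be analyzed based on Phase 1 SAS patients", where SAS is the safety analysis set, and it censors patients without a recorded death when they were last known to be alive.

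**The concern.** One event has two different consequences. Stopping the drug leaves a patient in the study and under follow-up; leaving the study ordinarily ends data collection. A site that takes Section 7.4.2 at its word, and finds in Section 8.3 that the treatment-stopping list also serves as the list for removal from the study, has two passages pointing towards closing the patient out.

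The loss would not be random. It would fall on patients removed because of toxicity, whose later risk of death or transformation may differ from that of the others. OS and AML progression would then be censored early for a reason that may be linked to the outcome, which Kaplan-Meier estimation assumes is not the case.

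**Working it through.** No stated sample size, power or error rate rests on this point, so the check is a comparison of passages, with arithmetic only for scale.

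**1. The passages side by side**

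| Protocol location | Study treatment | Study participation | Force |
|---|---|---|---|
| 7.3.5 | stops | not addressed | mandatory |
| Table 4, footnote b | stops | not addressed | mandatory |
| 7.4.2 | stops by implication | ends | mandatory |
| 8.3.1 | can stop | not addressed | worded with *may* |
| 8.3 | points to the 8.3.1 list | same list serves as criteria for removal | worded with *may* |
| 8.3.2; 12.2.2; Table 6, b and c | 8.3.2 starts from treatment having stopped | follow-up continues for at least a year | mandatory, no DLT exception |

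There are two conflicts: whether a DLT patient stays in the study (7.4.2 and 8.3 against 8.3.2, 12.2.2 and Table 6), and *will* in 7.3.5 and 7.4.2 against *may* in 8.3.1.

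**2. Is study simply shorthand for treatment in 7.4.2?** Nothing in the Protocol says so. Appendix 5, on pregnancy, treats stopping the study drug and withdrawal from the study as alternatives. Section 7.4 also speaks of the study, not treatment, for certain events at the -1 dose level. The text does not settle the meaning.

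**3. What a literal reading would cost per patient.** DLTs fall within 28 days of starting treatment. One year of six-monthly contacts is 12/6 = 2 contacts, both after that window. A surviving DLT patient closed out in Cycle 1 could miss both, and the OS rule would censor that patient near close-out.

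**4. How many patients.** Table 14 (Appendix 2) gives the average number of patients with a DLT and the average number per trial:

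- Scenario A: 5/21.3 = 23.5%
- Scenario B: 5/20.8 = 24.0%
- Scenario D: 4.7/21.1 = 22.3%
- Scenario C: 0.1/26.2 = 0.4%

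The table does not agree with itself. Scenario C has a constant 5% DLT rate, which gives 0.05 × 26.2 = 1.31 expected DLTs, not 0.1. The patient counts by toxicity interval should add up to the trial size but do not: A 0.3 + 10.3 + 0 = 10.6 against 21.3; B 0.9 + 5.2 + 1.8 = 7.9 against 20.8; C 0.3 against 26.2; D 1.8 + 3 + 5.4 = 10.2 against 21.1.

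As a cross-check on assumed rates, take the planned 30 Phase 1 patients. An average DLT rate of 5% gives 30 × 0.05 = 1.5 patients with a DLT; the edges of the target interval give 30 × 0.16 = 4.8 and 30 × 0.33 = 9.9. The last figure would need an average rate at the top of the target interval across all patients, which is unlikely when escalation starts at the lowest planned level.

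**5. From DLT patients to affected endpoints.** Each of these shrinks the count:

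- A DLT that is itself a death loses no OS information.
- Section 13.1.9.1.1 dates Phase 1 OS from initial dosing at the recommended Phase 2 dose (RP2D) level or the level just below it. Intra-patient escalation is barred (Section 7.3.1, Calculation of Dose), so a DLT patient treated only above the RP2D appears to have no OS start date under that sentence.
- AML progression is analysed in the efficacy evaluable set (Section 13.1.9.1.2.9), which needs a post-baseline response assessment (Section 13.1.5). Some patients stopped in Cycle 1 may not qualify.

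**6. What is untouched.** A patient enters the DLT analysis set on the DLT alone (Section 13.1.5), so DLT counts and the Bayesian logistic regression model (BLRM) do not depend on later follow-up. The Phase 2 response rate does not rest on the disposition of Phase 1 DLT patients.

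**The case against.** The strongest reply is that the Protocol already secures the follow-up. Section 8.3.2 is triggered by permanent discontinuation of treatment, and anyone taken off the study has stopped treatment. Section 8.3 itself requires an end-of-treatment visit in every case except withdrawal of consent, and asks for the end-of-study assessments where possible. Table 6 and Section 12.2.2 count follow-up from the first dose. This stands as far as it goes: it shows that loss is possible rather than certain. It does not remove the conflict, because no passage says which rule prevails.

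Three stronger readings are tempting and should not be drawn.

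- A reader might infer that 22% to 24% of Phase 1 patients would lose their follow-up. That needs every site to prefer 7.4.2 over 8.3.2, and it ignores the reductions in step 5.
- A reader might infer that follow-up of cardiac and hepatic events, the events of special interest, would also be closed early. Section 12.1.6.2.1 and Table 6 footnote p have adverse events followed to resolution, baseline or a stable state; Section 12.1.5.5 has clinically significant laboratory values repeated; and Section 12.1.6.4.1 keeps related serious events reportable after the 30-day window. The documents do not support a general loss of safety follow-up.
- A reader might take *may* in Section 8.3.1 as discretion to keep a DLT patient on drug. That list also contains death and withdrawal of consent, so it can be read as a catalogue of reasons. The difference from *will* elsewhere still needs reconciling, but it is the weaker of the two conflicts.

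**Conclusion.** The contradiction is real and sits in an operative rule. Read literally, Section 7.4.2 could end survival and AML follow-up in surviving DLT patients, with early, toxicity-related censoring of two Phase 1 secondary endpoints. Read through Section 8.3.2, nothing is lost.

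The number affected is uncertain. The Table 14 share is an upper guide for scenarios A, B and D, taken from a table that is internally inconsistent; few patients would be affected if toxicity is low. The conclusion assumes only that some sites would act on 7.4.2 as worded.

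The practical effect is now small. SAP Section 2 reports that the study was terminated after two patients were enrolled, dosed and discontinued, and plans by-patient listings with no OS or AML analysis. This is a defect in the Protocol as written, worth correcting in any further use of the text.

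**What to change.** In Sections 7.4.2 and 8.3, state separately what a DLT means for study treatment and for study participation. Add that patients who stop treatment continue follow-up per Section 8.3.2 and Table 6 unless they withdraw consent to it, are lost to follow-up or die. In Section 8.3, stop using the Section 8.3.1 treatment list as the criteria for removal from the study. Check the sentence in Section 7.4 on events at the -1 dose level for the same wording.

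The sponsor must also reconcile Sections 7.3.5, 7.4.2 and 8.3.1 and Table 4 footnote b on whether and how treatment stops after a DLT. No clinical rule is proposed here.

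The cost is a wording change. The follow-up contacts are already scheduled in Table 6, and no analysis, sample size or dose-escalation rule changes.

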7.5. Procedures

The planned schedule of assessments, including all treatments and procedures and their timing, is presented in [Table 6](#). Adherence to the study design requirements, including those specified in the Schedule of Assessments is essential and required for study conduct.

Table 6: Schedule of Assessments

Procedures / Tests	Pre-dose		Cycle 1		Cycle 2		Cycle 3,4		Cycle 5 and beyond		End of Treatment ^a	Follow Up ^{b,c}
	28 D	72 Hr	D1 (±1)	D2 (±1)	D8 (±1)	D15 (±1)	D1 (±2)	D8 (±2)	D15 (±2)	D1		
Informed consent ^d	X											
Eligibility evaluation ^e	X											
Medical history ^f	X											
Prior MDS treatments	X											
Transfusion history - 12 weeks prior to Cycle 1 Day 1	X											
Transfusion Data Collection and Anemia Assessment												
Complete physical exam	X										X	X
Abbreviated physical exam		X		X	X	X	X	X	X	X		
Vital signs	X		X	X	X	X	X	X	X	X	X	X
ECOG PS	X		X			X			X	X	X	X
ECHO or MUGA scan ^g	X					X			X	X		
Cardiac markers	X		X		X	X		X	X	X	X	X
MRI (Heart and Liver) ^h	X								X			X
NYHA classification	X		X		X	X	X	X		X	X	X
Hematology	X ⁱ		X		X	X	X	X	X	X	X	X

Continuous, until 30 days after last TP-0184 dose administration or EOT visit, whichever occurs later.

Procedures / Tests	Pre-dose		Cycle 1			Cycle 2			Cycle 3,4			Cycle 5 and beyond		End of Treatment ^a	Follow Up ^{b,c}
	28 D	72 Hr	D1	D2 (±1)	D8 (±1)	D15 (±1)	D1	D8 (±2)	D15 (±2)	D1	D15 (±2)	D1	D15 (±2)		
Chemistry	X			X	X	X		X	X		X		X	X	X
Coagulation	X				X			X		X		X	X	X	X
Pregnancy test (If Applicable) ^j	X				X			X		X		X	X	X	X
Urinalysis	X				X			X		X		X	X	X	X
Iron panel (markers of iron regulation) ^k	X			X	X	X		X		X	X ^k	X	X	X	X
Hepcidin	X					X			X		X		X	X	X
Cytokines ^l	X					X				X ^l		X ^l		X ^l	X ^l
SMAD-1, 2, 3, 5 and 8, in PBMCs ^m	X		X		X					X ^m		X		X	X
SMAD-1, 2, 3, 5 and 8 in biopsy/aspirates ^m	X									X ^m			X	X	X
MDS Disease Assessment ⁿ	X									X			X	X	X
Prior and Concomitant medications / procedures															
Assessment of AEs ^{o,p}															
TP-0184 administration				X	X	X	X	X	X	X	X	X	X	X	X
BFI	X			X			X			X		X	X	X	X
Ph1 Safety ECG ^q	X	X	X	X	X	X	X	X	X	X	X	X	X	X	X

Continuous, until 30 days after the last dose of TP-0184 or EOT visit, whichever occurs later.

Procedures / Tests	Pre-dose		Cycle 1			Cycle 2			Cycle 3,4		Cycle 5 and beyond		End of Treatment ^a	Follow Up ^{b,c}
	28 D	72 Hr	D1 (±1)	D2 (±1)	D8 (±1)	D15 (±1)	D1 (±2)	D8 (±2)	D15 (±2)	D1	D15 (±2)	D1		
Ph1 Intensive Holter ECG monitoring ^f		X						X						
Ph1 PK		X	X	X	X	X	X	X	X					
Ph2 Safety ECG ^g	X					X	X	X	X	X				
Ph2 PK						X	X	X	X	X				
Hematopoietic Stem Cell Transplant														
Overall Survival														
MDS Progression / Transformation to AML														

First dose TP-0184 through Follow-up Visit

- Collect for at least one year from the start of TP-0184 treatment
- Collect for at least one year from the start of TP-0184 treatment

Abbreviations: AE = adverse event; AML = acute myeloid leukemia; BFI = Brief Fatigue Inventory; ECG = electrocardiogram; ECHO = echocardiogram; ECOG = Eastern Cooperative Oncology Group; EOT = end of treatment; MDS = myelodysplastic syndromes; MRI = magnetic resonance imaging; MUGA = Multiple-gated acquisition; NYHA = New York Heart Association; PBMC = peripheral blood mononuclear cell; PK = pharmacokinetics

Note: The following will be collected locally and sent to the central lab: **Cardiac markers, iron panel, Hep-25, IL-6, PBMC-SMAD, BMA-SMAD, BMA-Genetic, TGF-beta-1, PK/Metabolites, Bone marrow biopsy.** Refer to the Laboratory Manual for further details.

^a If a patient discontinues study treatment, an End of Treatment visit should be conducted within 14 days (within 3 days) of the last dose of TP-0184 or within 14 days of the decision to discontinue TP-0184 treatment. If the decision is made at a regular per protocol scheduled visit, that visit may be considered the End of Treatment visit.

^b Patients must have a safety evaluation 30 days (+ 7 days) after the last dose of TP-0184.
^c Survival follow-up is performed every 6 months. Follow-up for progression of MDS to higher risk and / or transformation to AML and survival will continue for at least one year from start of treatment (Cycle 1 Day 1).

^d Informed consent must be obtained prior to conduct of screening evaluations.

^e Review all inclusion and exclusion criteria (Section 8) to determine if patient meets all eligibility criteria for enrollment into the study. Complete Eligibility Form and obtain Medical Monitor approval to enroll patient.

^f Collect and document a complete medical and disease history including initial histologically confirmed, current diagnosis of MDS and signs and symptoms of disease, and 12 weeks of transfusion history.
^g ECHO/MUGA scans will be performed every other cycle, such that days on which MRI scans are avoided.

^h MRI (iron quantification) of heart and liver is acquired locally and sent to Central Imaging (refer to the study-specific Imaging Manual), and will be performed at Screening and Cycle 3 only. MRI may also be performed ad hoc if signs/symptoms of iron overload are noted. For patients continuing on treatment beyond Cycle 6, MRI will be performed every 6 cycles for the duration of treatment and at the End of Treatment visit unless performed within 6 weeks of the visit. Heart MRI will be performed as secondary monitoring to ECHO/MUGA scans.

ⁱ Pre-treatment counts averages at least 2 measurements, per IWG Criteria.

^j Pregnancy testing (urine or serum) is performed for women of childbearing potential only.

^k Iron panel (serum iron, transferrin, soluble transferrin [STR], and TIBC) is collected by local laboratories and sent to the central laboratory. Ferritin will be used as a safety parameter and analyzed by local laboratories and the other iron metabolism parameters will be exploratory. Samples will be collected at pre-dose, Cycle 1 Day 8 and Day 22, Cycle 2 Day 1 and Day 15, Cycle 3 Day 1 and Day 15, then Day 1 of subsequent cycles and EOT.

^l CRP and EPO will be collected and analyzed at the local laboratory. IL-6 and TGF-beta 1 will be collected by the local laboratory and sent to the central laboratory. Samples will be collected pre-dose, Cycle 2 Day 1, Cycle 4 Day 1, Cycle 7 Day 1, then Day 1 of every 3 cycles thereafter (Cycle 10, etc.), and EOT.

^m SMAD-1, 2, 3, 5, and 8, in PBMCs and bone marrow biopsy/ aspirates: 1) PBMC's – using peripheral blood lymphocytes drawn; predose (with biopsy) and C1D8, C3D1, C4D1, C6D1, and at EOT; 2) Bone marrow biopsy/aspirate – Pre-dose, Cycle 4 Day 1, and at EOT (if performed for assessment of MDS progression); 3) Gene mutations in bone marrow biopsy/aspirates and/or peripheral blood samples – Pre-dose and at EOT.

ⁿ MDS assessments according to IWG MDS 2006 ([Appendix 6](#)) include hematology and bone marrow biopsy/aspirate at Pre-dose, Cycle 4 Day 1, and at EOT (if performed for assessment of MDS progression). For patients continuing on treatment beyond Cycle 6, response assessments will be performed every 12 months. NOTE: If the bone marrow biopsy and/or aspirate is nonproductive or not diagnostic, the procedure must be repeated. Six to 8 bone marrow slides should be prepared (in addition to fresh bone marrow samples) for study analysis.

^o Adverse events will be assessed according to the NCI CTCAE v5.0. When the grade is not available, refer to [Section 12.1.6.2.3](#).

^p Adverse event will be followed until either resolved, has returned to baseline, or is determined to be a stable or chronic condition.

^q Performed in Phase 1 Dose Escalation Only (at 6 hours after dose, and 10 minutes prior to PK collection at 6 hours).

^r Holter ECG: Cycle 1 Day 1: Approximately 1 hour prior to TP-0184 dose through Day 2 and Cycle 2 Day 15: Approximately 1 hour prior to TP-0184 dose through Day 16. Recordings will continue through 24 hours after the Cycle 1 Day 1 dose and after the Cycle 2 Day 15 dose.

^s Performed in Phase 2 Dose Expansion Only (prior to [but not less than 10 minutes before] any blood sample collection).

8. SELECTION AND WITHDRAWAL OF PATIENTS

8.1. Inclusion Criteria

Each patient must meet the following criteria to be enrolled in this study:

1. A documented diagnosis of lower risk MDS (IPSS-R Low, Intermediate) according to WHO 2016 classification, de novo or secondary.
2. Bone marrow biopsy and/or aspirate performed pre-dose to assess disease status and available for review *prior* to full screening review. If the bone marrow biopsy and/or aspirate is nonproductive or nondiagnostic, the procedure must be repeated. Bone marrow biopsy/aspirate performed \leq 12 weeks prior to baseline will not need to be repeated if results and a minimum of 6 slides are available.
3. Relapsed, refractory/resistant, intolerant, or inadequate response to ESA treatment, as defined by the following:
 - Relapse according to IWG 2006
 - Refractory/resistant – documented non-response or response that is no longer maintained to prior ESA-containing regimen, either as single agent or combination (eg, with G-CSF). ESA regimen must have been either:
 - Recombinant human erythropoietin (rHu EPO) \geq 500 IU/wk for at least 8 doses or equivalent

OR

 - Darbepoetin alpha \geq 300 μ g Q3W for at least 4 doses or equivalent
 - Intolerant – documented discontinuation of prior ESA containing regimen, either as single agent or combination (eg, with G-CSF), at any time after introduction due to intolerance or an adverse event.
 - Inadequate response – in the absence of transfusions support, patients under ESA treatment for at least 12 weeks that do not show a rise in hemoglobin of greater than equal to 1 g/dl.
4. Patients with 5q deletions are allowed only if they have failed or are intolerant to lenalidomide treatment.
 - Failure or intolerance to lenalidomide defined as clinical and cytogenetic responses to according to the international working group 2006 MDS: (1) absence of response; (2) bone marrow progression during treatment with or without prior response; (3) secondary failure (loss of prior hematological response without bone marrow progression); or, (4) intolerance (treatment discontinuation due to AEs, with or without prior response) based on investigator judgement ([Prebet 2017](#)).
5. Previous treatment for anemia with or without RBC transfusion support:
 - a. Low transfusion burden (LTb), defined as requiring less than 4 red blood cell units in the 8 weeks before treatment (and baseline hemoglobin $<$ 9.0 g/dL)

- b. High transfusion burden (HTb), defined as requiring 4 or more red blood cell units in the 8 weeks before treatment
- 6. At least 12 weeks of transfusion history immediately preceding the first dose of TP-0184. This transfusion data must include hemoglobin measured prior to transfusion (pre-transfusion Hgb).
- 7. Informed consent for trial participation from the patient appropriately in accordance with applicable ICH guidelines and local and regulatory requirements prior to the performance of any study related procedure.
- 8. At least \geq 18 years of age.
- 9. An Eastern Cooperative Oncology Group (ECOG) Performance Status (PS) score \leq 2.
- 10. A life expectancy of \geq 3 months (90 days) per the treating investigator.
- 11. Adequate major organ function meeting the following criteria on the basis of laboratory data within 28 days of first dose, during screening. If multiple data points are available, the most recent data acquired during the 28 days screening period will be used.
 - a. Serum creatinine: \leq 1.8 x the upper limit of the normal (ULN) range.
 - b. Total bilirubin \leq 1.5 x upper limit of normal (ULN) except in patients with Gilbert's syndrome. Patients with Gilbert's syndrome may enroll if direct bilirubin is \leq 2.0 x ULN. Elevated indirect bilirubin due to post-transfusion hemolysis is allowed.
 - c. Aspartate transaminase (AST) and alanine transaminase (ALT): \leq 2.5 x ULN.
 - d. Left ventricular ejection fraction (LVEF) \geq 45% by echocardiogram or multigated acquisition (MUGA) scan.
- 12. All previous therapy with ESAs, G-CSF, and GM-CSF must be discontinued \geq 14 days before Cycle 1 Day 1 dosing.
- 13. Twenty-eight-day washout period from prior treatment with cytotoxic chemotherapeutic agents, HMAs (hypomethylating agents), ImiDs (immunomodulatory imide drugs), luspatercept, and/or investigational drugs before study dosing for the patient begins.
- 14. Women of childbearing potential (WOCBP) with a negative serum or urine pregnancy test within 5 days prior to the first dose of TP-0184.
- 15. Non-fertile or agree to use an adequate method of contraception while on study and for 7 months after the last dose of TP-0184, and a negative pregnancy test (if female of childbearing potential) and not currently nursing; males agree to use an adequate method of contraception while on study and for 4 months after the last dose of TP-0184.
- 16. Ability to comply with the requirements of the entire study and accessibility for treatment and follow-up.
- 17. Agreement not to participate in other interventional clinical studies during participation in this trial, while on study treatment. Patients participating in surveys or observational studies are eligible to participate in this study.

